13.7 Adverse Event review process

All adverse events will be reviewed by the study coordinator. This review will include the determination whether the adverse event meets regulatory reporting requirements.

Table 1: Adverse Event reporting requirements						
Serious Adverse Device Effects (SADE)						
Investigator submit to:						
PI/study coordinator	Immediately after the investigator first learns of the event.					
MEC	Reporting timeframe as per local MEC requirement.					
PI submit to:						
Regulatory Authorities	Reporting timeframe as per local requirement.					
MEC	Submit to MEC per local reporting requirement.					

13.8 Outcome

The outcome of the AE should be classified according to the following definitions:

- Ongoing: the event is ongoing and has not yet resolved.
- Recovered / resolved: the event has resolved without sequelae (no further symptoms are present and no treatment is being received by the patient).
- Recovered / resolved with sequelae: the event has resolved but there may be lingering effects present (e.g., a scar following a cut or abrasion).
- Fatal: the patient died as a result of the event. This code should only be used for the event that caused the death, not any event that was present at the time of the patient's death. Fatal events require immediately reporting to the sponsor (or an authorized representative).
- Unknown: may only be used in the event that the patient is lost to follow-up and no reliable data can be obtained.

All efforts should be made to classify the AE according to the above categories.

13.9 Follow-up of Adverse Events

All AEs occurring during the study are to be followed up in accordance with good medical practice until resolved or judged no longer clinically significant, or if a chronic condition, until fully characterized. All follow-up results are to be reported in the eCRF. Assessment should be made at each visit (or more frequently, if necessary) of any changes in severity, the suspected relationship to the device, the interventions required to treat it, and the outcome.

13.10 Patient Death

All patient deaths during the investigation should be reported to the principal investigator within 24 hours.

Notification of death should include a detailed statement of the pertinent events and be signed by the investigator or authorized personnel in addition to the appropriate CRF(s) ("Patient Death" and "Adverse Event" forms where applicable). It is the investigator's responsibility to notify the appropriate Ethics Committees (EC). Details of death should be included in a letter to the principal investigator summarizing the patient's course since enrolment in the study and the following information (Patient's anonymity will be protected on all documents provided):

- Date and time of death;
- Place death occurred (e.g. hospital, nursing home, patient's home);
- Whether death was witnessed;
- Cause of death (if known);
- Any other circumstances surrounding the death;
- Approximate time interval to death from the initiating event:
- Whether it was device or procedure related;
- Device configuration at time of death;
- Autopsy report (if performed).

If available, also provide clinical notes and witness statements. All appropriate case report forms must be completed.

14. Study Termination

If a patient wishes to withdraw from the study at any time, he/she would be able to do so without having to justify it and without affecting his/her relationship with the investigator. Also, an investigator may withdraw a patient from the study at any time if he/she thinks it is in the patient's best interest. In either case, the investigator will be requested to complete a "Termination Form" for any patient that leaves the study for whatever reason.

15. Administrative Procedures

15.1 Regulatory and ethical considerations

This study will be conducted according compliance with the Declaration of Helsinki and national law.

15.2 Informed Consent

Before a patient can participate in the study, the patient must give written informed consent (witnessed, where required by law or regulation). The informed consent process will be in accordance with ISO 14155, the Declaration of Helsinki, the European Data Protection Directive and local regulatory requirements. Patient informed consent (PIC) forms will be based on a master document (see Appendix 24.2), and must be submitted to the EC. Each potentially eligible patient will be informed of the study's objectives and overall requirements. Prior to conducting any study-specific procedures, the investigator will explain the study fully to the patient. Patients will be informed that they take part in a study comparing different conditions of stimulation. If the patient is willing to participate in the study, he/she will be requested to give written informed consent after being given sufficient time to consider his/her participation and the opportunity to ask for further details. The PIC

Protocol: Occipital nerve stimulation in medically intractable, chronic cluster headache CME Protocol number: 10.016 Version 1.11 dd. 26-09-2018 will be signed and personally dated by both the patient and the investigator. A copy of the signed form will be provided to the patient, and the original will be retained with the source documents.

15.3 Ethics Committee Requirements

Before initiation of the study at a given site, approval of the protocol, PIC, and any information presented to potential patients must be obtained, in accordance with the declaration of Helsinki, from the appropriate EC. A signed and dated statement that the protocol and informed consent have been approved by the EC must be given to the coordinating clinical investigator before study initiation. This approval must include the protocol and informed consent versions numbers to ensure use of the approved study documents. If any amendments to any of these documents occur during the study, approval must be obtained prior to their implementation. The investigator is responsible for ensuring that these actions occur. The EC is required to keep the sponsor application for at least 3 years after the completion of the study.

15.4 End of the Study

For administrative and safety reporting purposes, the end of the study will be defined as the last visit of the last patient. This provides for a single and conservative definition across all study sites.

15.5 Patient confidentiality

The investigator must ensure that the patient's anonymity is maintained. All data and measurements on participants in this trial will be entered via and managed by a secure data management application, ProMISe, of the department of Medical Statistics & BioInformatics of the LUMC. Data are accessible only via secure internet connections, using the Internet Explorer browser and access is limited to explicitly authorized users each of whom has his or her personal username and password. All access to the system is fully audited and logged and all changes can be traced back to their origin. The ProMISe system also performs routine quality checking and error reporting. The study coordinator has full access to the system. The randomisation

table is however fully shielded from all personnel except the trial statisticians and implanter/ case manager. ProMISe is a generic clinical data management system and extensively tested through its application in over 100 clinical registries and trials in Europe. Documents not for submission, such as signed PICs, should be maintained in strict confidence by the investigator. The sponsor will ensure that no patient will be identifiable either from the final report or published results.

16. Statistical methods

16.1 The aim of the study

[1] to prove that the treatment has a beneficial effect over follow-up time since start of treatment

[2] after [1] has been established, to prove that there is a dose-response effect.

While (1) may be ascribed (at least in part) to a placebo effect, we believe that (2) cannot, since its associated effect measure is based on a between group comparison with random allocation to which the patient should be sufficiently blinded.

16.2 Endpoints

The primary endpoint is the mean attack frequency (MAF). Let MAF0 and MAF6 denote the MAF at baseline and the MAF at six months for a given patient. MAF0 is the baseline value for each individual patient of the primary endpoint and hence will be taken into account in the analyses as a covariate; although the primary comparison is a randomised one and MAF0 strictly speaking does not need to be taken into account, incorporating this value into the analyses will increase power and allows secondary analyses with respect to possible interaction between the treatment and the baseline level.

The MAF has a skewed distribution, and therefore we will take the (natural) logarithm in our analyses. If case MAF6 is equal to zero, we will add the minimal possible value of 0.25 (corresponding to a single attack per month) to allow taking the logarithm.

The analyses will take the general shape of a regression analysis with lnMAF6 as the dependent variable, lnMAF0 as the covariate and treatment as a fixed factor. An interaction between treatment and lnMAF0 will be added in a secondary analysis.

We assume the following model: $\ln MAF6 = a + b \ln MAF0 + c \operatorname{Treat}$, where Treat=0 for 30% stimulation and Treat=1 for 100% stimulation, thus being an indicator variable for the randomly allocated arm.

First we use an F test to evaluate (at the 5% level) the null-hypothesis

(1) H₀1: a=0 & b=1 & c=0

(effectively comparing this model to the null-model: lnMAF6=lnMAF0 in both randomised groups)

Rejection of this null-hypothesis means that we have confirmed a stimulation effect over time. Now, ONLY if (1) is rejected, do we test the following three nullhypotheses

(2a) H₀2a: a=0 & b=1 conditional on Treat=0 (30% stimulation)
(2b) H₀2b: a=0 & b=1 conditional on Treat=1 (100% stimulation)
(2c) H₀2c: c=0 (no stimulation intensity effect)

Rejection of (2c) means that we have confirmed a dose-response effect, in other words a difference between 30% and 100% stimulation.

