16.3 Multi testing correction

We claim that upon rejection of (1), we may simultaneously test (2a), (2b) and (2c) at the 5% level, while maintaining the probability of falsely rejecting a single null hypothesis at 5% (so without the need for correction for multiple testing). This follows from the so-called closed testing principle (42). The underlying idea is that if null hypothesis (1) is false, then *at most one* of (2a), (2b) and (2c) can be true. The

Protocol: Occipital nerve stimulation in medically intractable, chronic cluster headache CME Protocol number: 10.016 Version 1.11 dd. 26-09-2018 closed-testing principle has been applied before in clinical trials but not very often (43). The method is more powerful than the more familiar "gate keeping" procedure, where we test hypotheses (1), (2c), (2b) and (2a) in order, and stop as soon as we fail to reject one.

The issue of multiple testing in biomedical research in general and in clinical trials in particular, is discussed by Bender and Lange (44).

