16.4 Power and sample size

Because of limited information about the distribution of the MAF for our specific group of patients, we conducted a small pilot study. We found a MAF of 26.42 attacks per week, with a standard deviation of 15.38. These findings did not differ very much from figures given by Burns et al. (7). These numbers correspond to lnMAF having a a mean of 3.13 and a standard deviation of 0.54.

We expect (MAF6 – MAF0) to be -9 on average in the 100% stimulation group, while we expect no reduction in the 30% stimulation group. This corresponds to (\ln MAF6 – \ln MAF0) being -0.42 on average in the 100% stimulation group.

If we assume that lnMAF0 and lnMAF6 are positively correlated, then the standard deviation of Delta = (lnMAF6-lnMAF0) would be in the range from 0.54 to $\sqrt{2}$ *0.54=0.76. Powering in terms of this Delta is a fair approximation to the regression analysis model; in fact, if the coefficient b would be equal to 1, the calculations would be identical.

Note that tests (1), (2a) and (2b) are in essence paired tests, comparing for each patient a change with respect to baseline. Test (2c) is an independent, two sample test because we compare the two treatment arms. Consequently, the test for (2c) will be the least powerful and so we performed our power analysis for that test. We did verify that all other tests are more powerful.

We attach the results of our power analysis. We conclude that if the standard deviation is 0.54 and the average of (lnMAF6-lnMAF0) is about -0.42, then 60

Protocol: Occipital nerve stimulation in medically intractable, chronic cluster headache CME Protocol number: 10.016 Version 1.11 dd. 26-09-2018 patients in each arm will allow us to detect the difference with probability 98%.

Taking a possible 20% drop-out rate into account, we propose a total study size of 144 divided equally between both arms.

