16.5 Analyses

We will use an intention to treat approach in all our primary analyses. A per protocol analysis will be undertaken if substantial deviations from the allocated treatment or a substantial amount of missing values are observed. In all cases the per protocol analyses will serve as a "sensitivity analysis" as intended by the ICH9 guidelines and a further support for proper interpretation of the ITT conclusions.

Patients switching to steroids will be withdrawn from further data collection but are retained in the study as such. Their MAF will be included up to the time they started the new medication.

Apart from the primary analyses which focus on a specific time point (6 months), secondary analyses will take the full repeated measurements structure into account, including the 6 months values. We use a mixed model for repeated measurements with time since randomisation as a fixed covariate (or factor), lnMAF0 as a

continuous covariate and Treat as a fixed factor. We will apply an AR1 covariance structure unless the data prove this to be untenable. This model is a direct extension of the simple regression model used to test the primary hypotheses and allows estimation of treatment effect over time, including possible interactions. We will also analyze the data using generalized estimating equations (GEE), aiming to consolidate the results from the mixed model analysis.

The mixed model will take the missing values into account in a natural way, assuming of course missingness at random. A sensitivity analysis will be undertaken to verify this assumption.

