16.6 Randomisation and blinding

Patients are randomised using a variable blocked stratified balanced design. The entire randomisation is generated before the first patient enters the trial and fixed. The randomisation table, although stored with the trial data base, is not accessible by users of the data management system except for the trial statistician and the implanter and casemanager. When a patient is entered into the (web based) data management system, the eligibility criteria are checked and the required stratification variables are specified. A request for randomisation is generated by the system and the next available record with the correct stratification values in the hidden randomisation table is allocated to the patient; both patient and randomisation record have a unique key which is stored both in the data tables and in the randomisation table. In the clinical data base the fact that the patient has been randomised, is made known by storing a random key which points to the record in the randomisation table. However, the web based interface does not allow any data manager or clinician to see the randomisation result if not authorized so by the very design of the trial. When the study data have to be analyzed according to randomised treatment, the randomisation table can be extracted from the data base by the statistician and joined to the clinical data extracted by the data manager of the trial. In case of emergency the statistician or implanter can either log on to the system and

retrieve the randomisation of a patient via his (authorized) account or the randomisation table can be viewed directly in case the internet connections break down (but only from within the dep. of Medical Statistics). A backup of the Protocol: Occipital nerve stimulation in medically intractable, chronic cluster headache CME Protocol number: 10.016 Version 1.11 dd. 26-09-2018 randomisation table is by definition assured since the entire data base is back up every day.

17. Risk assessment

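### Randomisation is stratified, but the factors are not named and are not in the primary regression or the mixed model; if they are prognostic beyond baseline, the dose-response test is conservative, with almost no effect on power

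*Combined protocol and SAP*

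**What the plan says.** Section 16.6 describes the allocation: "Patients are randomised using a variable blocked stratified balanced design". When a patient is entered in the system, "the eligibility criteria are checked and the required stratification variables are specified". The text available for review does not say which variables these are.

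Section 16.2 describes the primary analysis as a "regression analysis with lnMAF6 as the dependent variable, lnMAF0 as the covariate and treatment as a fixed factor" and then writes the model out: lnMAF6 = a + b·lnMAF0 + c·Treat. Test (2c), c = 0, is the comparison of 100% with 30% stimulation.

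The secondary mixed model in 16.5 follows the same pattern: besides time, it has the log baseline frequency as a "continuous covariate and Treat as a fixed factor". The GEE analysis planned there has no separate covariate list. None of these descriptions contains a stratum term, and nothing explains its absence.

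**The concern.** Stratified blocking keeps the arms balanced within strata, so most between-stratum variation in outcome drops out of the estimate of c. A model without strata still counts that variation as residual, and the reported standard error of c is then larger than its true sampling error. This happens only if the strata explain lnMAF6 beyond lnMAF0. If the stratifier is baseline attack frequency, for example, lnMAF0 already carries it.

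At stake is the calibration of one interval, not validity. It is, however, the interval for c, and section 16.1 rests its argument against a placebo explanation on that between-arm contrast. With the factors unnamed, a reader cannot judge whether the interval is too wide, or by how much.

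**Working it through.** **1. Inputs.** From 16.4: SD of lnMAF 0.54, difference 0.42 on the log scale, 60 per arm, stated power 98%. Also from 16.4: "Taking a possible 20% drop-out rate into account, we propose a total study size of 144 divided equally between both arms", which leaves 144 × 0.8 / 2 = 57.6 per arm. The 5% level is from 16.3; two-sided testing is assumed. The share R² of the residual variance of lnMAF6 (given lnMAF0) that the strata explain is not in the documents. It is varied from 0 to 0.30 as an assumption.

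**2. The plan's power.** nc = 0.42 / (0.54 × √(2/60)) = 4.26, and Φ(4.26 − 1.96) = 98.9%, in line with the stated 98%. At 57.6 per arm it is 98.7%.

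**3. Residual SD of the planned regression.** Section 16.4 says "the standard deviation of Delta = (lnMAF6-lnMAF0) would be in the range from 0.54 to" 0.76. With equal SDs of 0.54 and correlation ρ, the change-score SD is 0.54√(2(1−ρ)) and the residual SD is 0.54√(1−ρ²).

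| ρ | Change-score SD | Residual SD | Power at 57.6 per arm |
|---|---|---|---|
| 0 | 0.76 | 0.540 | 98.7% |
| 0.25 | 0.66 | 0.523 | 99.1% |
| 0.5 | 0.54 | 0.468 | 99.8% |

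So the 0.76 applies to the change score. The regression's residual SD is at most 0.54.

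**4. Omitting strata, by formula.** Under perfect balance the true variance of the estimate of c is (1−R²) times the reported one. True size is 2(1 − Φ(1.96/√(1−R²))) and the width ratio is 1/√(1−R²). For R² of 0.05, 0.10, 0.20 and 0.30, size is 4.4, 3.9, 2.8 and 1.9%, and the interval is 2.6, 5.4, 11.8 and 19.5% too wide.

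**5. Simulation.** 144 randomised, 20% random loss, assumed blocks of 2/4/6, equal-probability strata, 20,000 runs per cell. Monte Carlo error is about 0.15 points on size and 0.1 on power. Size and width cover 2 to 8 strata; the power columns are for 4 strata at ρ = 0.

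| R² | Size of (2c) as written | Interval wider by about | Power as written | Power adjusted |
|---|---|---|---|---|
| 0 | 4.8–5.0% | 0% | 98.5% | 98.4% |
| 0.05 | 4.4–4.7% | 2% | 98.6% | 98.8% |
| 0.10 | 4.1–4.3% | 5% | 98.7% | 99.1% |
| 0.20 | 3.2–3.4% | 11% | 99.0% | 99.6% |
| 0.30 | 2.4–2.8% | 19% | 99.2% | 99.8% |

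With strata in the model, size is 4.8–5.3%. Size as written is a little nearer 5% than in step 4 because drop-out disturbs the balance. Over ρ from 0 to 0.5 and 2 to 8 strata, power as written is 98.3–99.9%, and adjusting changes it by −0.2 to +0.7 points.

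**6. Interval in absolute terms (4 strata).** The half-width is 0.200 as written, against 0.190, 0.180 and 0.168 adjusted at R² of 0.10, 0.20 and 0.30. If c were estimated at −0.42, the ratio of attack frequencies would be exp(−0.42) = 0.66. Its interval would be exp(−0.62) to exp(−0.22), 0.54 to 0.80, as written. Adjusted at R² = 0.20, it would be exp(−0.60) to exp(−0.24), 0.55 to 0.79.

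**7. Does the closed test survive an adjusted (2c)?** Any two of (2a), (2b) and (2c) together still give a = 0, b = 1, c = 0, which is the null of (1). The simulation used 4 strata, R² of 0 / 0.10 / 0.20 / 0.30, and (1), (2a) and (2b) as written:
- Null of (1) true: any false rejection at most 5.0 / 4.6 / 4.2 / 3.8%.
- Both arms down 0.42, so only c = 0 holds: false rejection of (2c) 5.2 / 5.1 / 4.9 / 5.1% adjusted, against 5.1 / 4.2 / 3.2 / 2.5% as written.
- Only (2a) true: false rejection 4.8 / 4.5 / 4.5 / 4.2%.

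**The case against.** The strongest reply is that no harm is shown. The estimate of c is unbiased, errors are on the safe side and power hardly moves. The width penalty depends on an R² that the documents do not give and that may be 0. All of this stands, and it is why the point is minor.

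The strata may be listed in the case report forms (appendix 24.1), which appear here only as a heading. That would settle the naming, but not their absence from the models.

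Section 16.2 also treats covariates as optional in a randomised comparison and includes MAF0 mainly for power. By that criterion, leaving out strata that add under one point of power is defensible. The plan does not make this argument, though, and it does not address the interval.

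Finally, (1), (2a) and (2b) need a single intercept for a = 0 to have its meaning, and stratum terms would remove it. This is a real constraint, and it means adjusting (2c) alone. The price is that the F test for (1) uses one estimate of c while another is reported. With 4 strata the two differ with an SD of 0.008 to 0.027, against a standard error of about 0.10, and error control holds.

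**Conclusion.** The concern holds, at minor weight. The trial randomises within strata and does not analyse by them. If the strata are prognostic beyond lnMAF0, test (2c) runs below its nominal 5% and the interval for c is wider than needed: about 2% at R² of 0.05, up to about 19% at R² of 0.30. If they are not, nothing is lost except clarity about the design.

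The limited effect on power rests on the plan's equal SDs of 0.54. Only if the residual SD of lnMAF6 given lnMAF0 reached 0.76, which is not the plan's figure, would adjusting add about 2.5, 5 or 7 points at R² of 0.10, 0.20 or 0.30. The figures further assume random drop-out, the block sizes used above and two-sided testing. None was calculated for the mixed model or GEE.

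**What to change.** - Name the stratification variables in the SAP.
- Add them as fixed factors to the regression that tests (2c) and, for consistency, to the mixed and GEE models.
- State that (1), (2a) and (2b) stay on the model as written and that the adjusted c is the one reported.
- Before unblinding, fix a rule for pooling sparse strata, or use a random effect if centre is a stratifier. The text does not say that it is, but under section 18.2 a recruitment site may expect as few as 4 to 8 patients a year.
- If the factors are left out on purpose, say so and give the reason.

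This takes three or four sentences once the strata are named, and the variables are already in the randomisation system. The statistical cost is a few of about 112 residual degrees of freedom (144 × 0.8 ≈ 115, less 3 parameters). In an unfavourable case of 20 uninformative strata, adjusting uses 19 degrees of freedom, widens the interval by about 3% and costs 0.6 points of power at residual SD 0.54. The pooling or random-effect rule limits that.

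### Tests (1), (2a) and (2b) fix the regression slope at 1, so they do not test mean change; with equal SDs at both times they reject in 97-100% of trials in which nothing changed on average.

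*Combined protocol and SAP*

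**What the plan says.** Section 16.2 assumes lnMAF6 = a + b lnMAF0 + c Treat. Test (1) is an F test of a=0, b=1 and c=0, described as "effectively comparing this model to the null-model: lnMAF6=lnMAF0 in both randomised groups". Its rejection is interpreted as follows: "Rejection of this null-hypothesis means that we have confirmed a stimulation effect over time". Only after that rejection does the plan test (2a) and (2b), which set a=0 and b=1 in the 30% and the 100% arm, and (2c), which sets c=0.

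Section 16.4 describes the first three tests this way: "Note that tests (1), (2a) and (2b) are in essence paired tests". It gives lnMAF a mean of 3.13 and a single SD of 0.54, and bounds SD(Delta) between 0.54 and sqrt(2) x 0.54 = 0.76. For low stimulation it says "we expect no reduction in the 30% stimulation group".

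Section 6 makes reduction from baseline the primary objective, and section 16.1 lists proof of benefit over time as the first aim.

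**The concern.** A paired test asks whether the mean of Delta = lnMAF6 - lnMAF0 is zero and leaves the slope free. Tests (1), (2a) and (2b) also require b=1, and b = rho x SD6/SD0, where rho is the within-patient correlation. If the mean and SD are the same at both times, then b = rho and a = 3.13(1 - rho). All three nulls are then false although attack frequency has not changed on average.

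For example, at rho = 0.5, a = 1.565. A patient at 3.67 (one SD above the mean) is expected at 1.565 + 0.5 x 3.67 = 3.40. A patient at 2.59 (one SD below) is expected at 2.86. The tests pick up this movement toward the mean.

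The F tests also have no direction, so a rise in attacks can reject them. Test (1) is the gate to everything else and, with (2a) and (2b), carries the section 6 objective. The placebo caveat in 16.1 does not cover the problem: a placebo response is a real mean improvement, and none is needed here.

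**Working it through.** **The plan's own figures.** An arithmetic mean of 26.42 and SD of 15.38 give a log SD of sqrt(ln(1 + (15.38/26.42)^2)) = 0.540 and a log mean of ln 26.42 - 0.540^2/2 = 3.128. The planned effect is ln(17.42/26.42) = -0.417. Power for (2c) with 60 per arm, SD 0.54 and difference 0.42 is 98.9%, against 98% stated. These inputs reproduce.

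**What the SD range implies.** SD(Delta)^2 = SD0^2 + SD6^2 - 2 rho SD0 SD6. With SD0 = SD6 = 0.54, SD(Delta) is 0.76 at rho = 0 and 0.54 at rho = 0.5. The upper limit sqrt(2) x 0.54 is the zero-correlation value only if the SD is 0.54 at both times. The planned range therefore corresponds to b from 0 to 0.5.

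**When b=1 would hold.** It requires SD6^2 = SD0^2 + SD(Delta)^2. That gives SD6 = 0.764 (rho 0.71) at SD(Delta) 0.54, and 0.935 (rho 0.58) at SD(Delta) 0.76. The plan gives no six-month SD.

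**Simulation.** 20,000 bivariate normal trials per setting, 60 per arm, mean 3.13 at both times in both arms. Test (1) is F(3,117). (2a) is run after the gate, either fitted within the arm, F(2,58), or as a contrast in the common-slope model, F(2,117). Percentage rejecting with SD 0.54 at both times:

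| rho = b | SD(Delta) | Test (1) | (2a) within arm | (2a) common slope |
|---|---|---|---|---|
| 0 | 0.76 | 100.0 | 100.0 | 100.0 |
| 0.5 | 0.54 | 100.0 | 97.3 | 100.0 |
| 0.7 | 0.42 | 97.2 | 80.0 | 97.0 |
| 0.8 | 0.34 | 85.8 | 58.6 | 85.0 |
| 0.9 | 0.24 | 52.7 | 27.4 | 50.3 |
| 0.95 | 0.17 | 27.2 | 12.3 | 24.5 |

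Rows below 0.5 in the table are assumptions outside the plan's SD range. A paired t test rejects in about 5% and test (2c) in 4.8-5.0%.

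**Closed-form check.** With equal SDs the noncentrality of test (1) is about N(1 - rho)/(1 + rho). At rho = 0.5 this is 120 x 0.5/1.5 = 40, giving a rejection rate above 99.9%. At rho = 0.9 it is 120 x 0.1/1.9 = 6.3, giving 53%. Within one arm at rho = 0.5 it is 60 x 0.5/1.5 = 20, giving 98%. These agree with the simulation.

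**Letting the spread grow (assumption), no mean change.**
- SD(Delta) held at 0.54, SD6 of 0.60, 0.65, 0.70 and 0.764 (b = 0.62, 0.72, 0.84 and 1.00): test (1) rejects in 96.9%, 73.6%, 27.7% and 5.1%.
- SD(Delta) held at 0.76: about 94% at SD6 0.76 and 5% at 0.935 (b = 1).

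**Other settings.**
- Restricting baselines to the entry minimum of 4 attacks per week (rho 0.5, 2,000 trials) barely changes the result: test (1) 99.95%, (2a) 96.7%, (2b) 97.1%.
- Under the planned effect (-0.42 at 100%, none at 30%) with equal SDs, (2a) rejects in 97-100% in the arm expected not to improve. A paired test there rejects in 5%.
- With a true rise of 0.10 in lnMAF in both arms (assumption), test (1) rejects in about 100% at rho 0 and 0.5.

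**The case against.** **The tests are valid for their literal nulls.** This is true, and the closed-testing argument in 16.3 holds for those nulls. The fault is in reading rejection as a stimulation effect.

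**The randomised comparison is what matters.** Section 16.2 calls the primary comparison a randomised one, (2c) keeps its level, and 16.1 rests the causal argument on it. Under the planned effect, (1) and (2b) reach the same answer with or without the change; (2a) is the decision that differs. This limits the harm to the before-after claims. Section 6, however, makes reduction from baseline the primary objective, so these claims are not exploratory.

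**The 97-100% rests on inputs the plan does not state.** Section 16.4 gives neither rho nor a six-month SD, and a positive correlation does not exclude rho above 0.5. This stands: the size is uncertain and can fall to 5%. But most of the plausible settings stay far above 5%, and the plan mentions b=1 only conditionally, in a remark on power: "if the coefficient b would be equal to 1, the calculations would be identical". The power output that 16.4 says is attached is not in the text. It might clarify the assumed correlation but is unlikely to alter the nulls.

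**The replacement has limits too.** A 2-df test of mean Delta is also non-directional: with the 0.10 rise it rejects in 41% at rho 0.5 and 24% at rho 0. Its closure needs equal expected baseline means, which randomisation guarantees for all patients randomised but not for completers. Assume 72 per arm and 20% drop-out, with drop-out in the 30% arm confined to above-average baselines (40% against 0%): the new gate rejects in 10-14% with no mean change, or 6-7% if the split is 30% against 10%. Both limits are real, and the fix has to address them. They are far smaller than the problem being repaired.

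**Conclusion.** The concern holds, and the text must change. Tests (1), (2a) and (2b) test whether six-month values follow the identity line, not whether the mean changed. With 60 per arm, SD 0.54 at both times and SD(Delta) in the planned range, they reject in 97-100% of trials without any mean change, so the gate gives almost no protection and its rejection cannot support the section 6 objective. The figures assume normal log frequencies and the linear model of 16.2. The exact rate depends on rho and the six-month SD, and is nominal only when b=1. Test (2c) is unaffected.

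**What to change.** - Define (1) as mean Delta = 0 in both arms (2-df F test), and (2a) and (2b) as mean Delta = 0 within the 30% and the 100% arm (paired t tests).
- Keep (2c) as the covariate-adjusted test of c=0 with b estimated.
- State in 16.3 that closure now relies on equal expected baseline means under randomisation, which makes each pairwise intersection equal to (1). Note that selective drop-out can weaken this among completers.
- Claim benefit only when the mean change is a reduction.
- Reword the interpretation in 16.2 to a confirmed change from baseline, described as an uncontrolled before-after comparison. The section 6 objective can stay, provided no before-after result is attributed to stimulation on its own.

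The cost is an amendment, with investigator agreement (19.3) and ethics approval before use (15.3). No new patients or data are needed. With no mean change the new gate rejects in 4.7-5.2%. Under the planned effect, at SD(Delta) 0.76 to 0.54, the new gate has 97-100% power and (2b) after it 97-100%. These powers assume a uniform normal shift of -0.42 and ignore the 0.25 substitution for zero counts. Before-after claims become harder to reach only where the mean has not changed.
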